[name]. will serve as Chair of the Data Safety and Monitoring Board (DSMB) which will be composed of another expert in clinical trials in alcohol treatment and an expert in statistical analysis of clinical trials. Twice annually the DSMB will review the progress of the study and frequency of serious adverse events.

- d. For multi-site studies for which the Yale PI serves as the lead investigator:
 - i. How will adverse events and unanticipated problems involving risks to subjects or others be reported, reviewed and managed?

All adverse events are reported using the Yale Institutional Review Board (IRB) standard template for reporting adverse events. The Yale Principal Investigator (PI) reviews all adverse events, classifies the attribution of adverse events (e.g., definitely, probably, possibly related; unlikely or unrelated) and grades the severity of the event, utilizing the FDA's definition of serious adverse events, on a 6-point scale (0=no adverse event or within normal limit; 1=mild; 2=moderate; 3=severe; 4=life-threatening; 5=fatal). Serious unanticipated or anticipated adverse

events will be reported immediately to the IRB and to NIAAA. Adverse events will be reported in summary form at least annually to the IRB. The summary will include the number of subjects enrolled and a summary of graded adverse events to date, using the chart format included in the Yale University DSMP template. The PI will evaluate all adverse events and determine whether the event affects the Risk/Benefit ratio of the study and whether modifications to the protocol (e.g., Risks to Subjects) or consent form (e.g., Risks and Inconveniences) are required.

ii. What provisions are in place for management of interim results?

No interim analyses will be performed

iii. What will the multi-site process be for protocol modifications?

There will be one protocol document and each participating institution will utilize that document. The Yale PI is responsible for the coordination of the approval of the protocol as well as its subsequent amendments and will be responsible to ensure that the sites are using the correct version of the protocol. The Yale PI will collect and maintain copies of all IRB approvals from each site and will collect and review conflicts of interest declarations made by the Site PIs.

9. Statistical Considerations: Describe the statistical analyses that support the study design.

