General considerations: This is a randomized, controlled, parallel group trial to evaluate the effectiveness of CM plus stepped care compared to TAU to reduce unhealthy alcohol use in HIV-infected individuals. Data analysis will be conducted by [name] and YCAS. The 6-month follow-up was chosen as the primary endpoint as we expect the most robust differences at this time and there is uncertainty in the shape of the treatment response over time. Average intervention group differences across all time points and slopes of change will be compared between groups in supportive secondary analysis. A type I error of 5% (two-sided) will be used to test for significance and analyses will be performed using SAS v9.2 (SAS Institute, Cary, NC).

Adequacy of sample size

The primary aim of the study is to determine whether CM plus stepped care will lead to a greater proportion of patients with PEth documented abstinence when compared to TAU. The primary outcome will be proportion of patients with self reported abstinence on Timeline Follow Back at 6 months, with PEth < 8 ng/ml at 6 months as a secondary outcome (Aim 1). Data from the TAU group in the **STEP** Trials, when restricted to those with a PEth > 20 ng/ml at baseline, reveals 11% spontaneous abstinence as assessed using PEth < 8 ng/ml at 6 months. We believe this provides a good estimate of the anticipated abstinence rate with TAU in the proposed trial. To detect a 15% difference (proportion demonstrating abstinence in CM plus stepped care of 26%) with 80% power at a two-sided 0.05 significance level, a sample size of 139 per group is required. Thus, we will enroll and randomize 348 patients to account for 20% dropout. Based on alcohol consumption in the TAU arms of the **STEP** Trials, and a standard deviation of 11.5, we will have 80% power to detect a difference of 3.9 in average drinks per week over the last 30 days, at 6 months. Data from the TAU group in the **STEP** Trials reveals that 29% of patients

experienced a 5-point decrease in the VACS Index at 6 months. With the proposed sample size, we will have 90% power, at a two-sided 0.05 significance level, to detect a 20% difference in this (Aim 2) outcome (proportion of patients who achieve a 5-point decrease in the VACS Index in CM plus stepped care of 49%). In our prior trials, including the **STEP** Trials, we have obtained completed 6-month assessments in 74-95% of enrolled subjects.^{60,61}

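### The stated inputs (11% versus 26%, two-sided 0.05, 80% power) need about 102 to 117 per group, not 139; and the 11% was measured by PEth, which is no longer the primary outcome

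*Combined protocol and SAP*

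**What the plan says.** All of the inputs stand in Section V, item 9, under Adequacy of sample size.

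- Control rate: earlier treatment-as-usual (TAU) data, restricted to patients with baseline PEth above 20 ng/ml, "reveals 11% spontaneous abstinence as assessed using PEth < 8 ng/ml at 6 months". The plan adds: "We believe this provides a good estimate of the anticipated abstinence rate with TAU in the proposed trial".
- Effect: a 15-point difference, so 26% in the contingency management arm.
- Size: "with 80% power at a two-sided 0.05 significance level, a sample size of 139 per group is required".
- Dropout: "Thus, we will enroll and randomize 348 patients to account for 20% dropout".
- Endpoint: "The primary outcome will be proportion of patients with self reported abstinence on Timeline Follow Back at 6 months", with PEth below 8 ng/ml as secondary. Section V, item 3 (Assessments, Overview) explains that the primary outcome was changed because PEth was hard to collect during the pandemic, on the DSMB's recommendation.
- Significance level: General considerations in item 9 says "A type I error of 5% (two-sided) will be used to test for significance". On interim results, item 8 says "No interim analyses will be performed".

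No sizing formula or test is named. No TLFB abstinence rate is given.

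**The concern.** This is the plan's only power statement for an abstinence outcome and the stated basis for randomizing 348 patients. It gives both rates, the significance level, the power and the sample size, so it can be checked, and the five figures do not agree. A reader would take 80% as the design power when the stated rates imply more, and cannot tell which figure is wrong.

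In addition, the control rate was measured on an outcome that is now secondary. Power for a fixed absolute difference falls as the control rate rises towards 50%. If the TLFB abstinence rate under usual care differs from 11%, the calculation says nothing definite about power for the current primary comparison.

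**Working it through.** **Inputs.** p1 = 0.11, p2 = 0.26, difference 0.15, mean rate 0.185, two-sided alpha 0.05 (z = 1.960), power 80% (z = 0.842). Equal groups are implied by a single size per group and by 348 = 2 × 174. The variance sum is 0.11 × 0.89 + 0.26 × 0.74 = 0.0979 + 0.1924 = 0.2903.

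**The dropout step reproduces.** 139/0.8 = 173.75, rounded up to 174; 2 × 174 = 348. So, as written, 139 is the evaluable number.

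**The 139 does not reproduce.** Size per group at 80% power:

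- Unpooled: (1.960 + 0.842)² × 0.2903/0.15² = 101.3, so 102.
- Pooled: [1.960 × √(2 × 0.185 × 0.815) + 0.842 × √0.2903]²/0.15² = 104.0, just over, so 105.
- Log odds ratio: ln OR = 1.045; (1.960 + 0.842)² × (1/0.0979 + 1/0.1924)/1.045² = 110.8, so 111.
- Fisher exact, by enumeration: 114 (power 0.803; 0.799 at 113).
- Pooled with continuity correction: (104.0/4) × [1 + √(1 + 4/(104.0 × 0.15))]² = 117.0, so 117.

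The largest is 22 per group short of 139.

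**Power for 11% versus 26%:**

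| Method | 139 per group | 129 per group |
|---|---|---|
| Continuity-corrected | 87.0% | 84.2% |
| Fisher exact | 88.0% | 85.2% |
| Log odds ratio | 88.1% | 85.6% |
| Pooled | 90.1% | 87.8% |
| Unpooled | 90.7% | 88.5% |

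The 129 is 0.74 × 174 = 128.8, from the lowest 6-month completion that the same section quotes. At 139 per group, 80% power corresponds to 11% versus about 24% (23.5% to 24.5% by method).

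**Possible sources of 139.** Each needs something the plan does not state.

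- Pooled formula at 90% power: 138.7. The plan says 80%.
- Pooled, 12% versus 25% at 80% power: 138.9. The plan says 11% and 26%.
- Pooled at 80% power with alpha near 0.017: about 139. The plan says 0.05 and has no interim efficacy look.
- Log-odds size already inflated for dropout: 111/0.8 = 138.75. The 20% would then have been applied twice.

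**The neighbouring statements hold at 139 per group.** Drinks per week (SD 11.5, difference 3.9): 80.4% by t test, against a stated 80%. VACS Index (29% versus 49%): 91.4% continuity-corrected and 93.2% pooled, against a stated 90%.

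**TLFB primary outcome.** The documents give no rate, so the TAU rate and an unchanged 15-point difference are both assumptions here. Power at 139 per group:

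| Assumed TAU rate | Pooled | Fisher exact |
|---|---|---|
| 5% | 97% | 97% |
| 8% | 94% | 93% |
| 11% | 90% | 88% |
| 15% | 85% | 82% |
| 20% | 80% | 77% |
| 25% | 76% | 73% |
| 30% | 74% | 70% |

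**The case against.** The best defence on the arithmetic is that all five methods are simple two-group comparisons, whereas Analysis for Aim 1 plans a repeated-measures generalized linear mixed model with covariates, site and possibly a treatment-by-stratum interaction. The larger size might include an allowance for that. This cannot be ruled out as history, but the plan states no such allowance, and the sentence presents 139 as following from the four figures beside it.

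A second point is that the error does no harm on its own terms: the trial is larger than its inputs require, and at the lowest quoted completion it still has 84% to 89% power for PEth. That is right. The arithmetic alone calls for a correction of wording.

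On the endpoint, the plan calls the 11% a good estimate of the TAU abstinence rate without limiting that to PEth, which can be read as carrying it over to TLFB. That reading is possible, but the rate is explicitly PEth-based and the carry-over is not stated. The TLFB result also depends on the method: at a 20% TAU rate, pooled power is just above 80% and Fisher exact is below it, so both are shown.

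**Conclusion.** The concern holds. By standard two-proportion methods, 11% versus 26% at two-sided 0.05 and 80% power needs 102 to 117 per group. With 139 evaluable per group, the power for those rates is about 87% to 91%. Which figure was misstated cannot be determined from the documents. The error is conservative for PEth and changes neither the total of 348, the type I error nor the analysis.

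For the current primary outcome the power is not shown. If the 11% applies to TLFB, the trial has ample power for a 15-point difference. If the TAU rate by TLFB is about 20% or more, power for the same difference is at or below 80%. This rests on 1:1 allocation, 139 evaluable per group and, for TLFB, on assumed rates and an assumed difference.

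**What to change.** Keep 348 and revise the paragraph in Section V, item 9:

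1. Identify the method and inputs that gave 139, including whether it already contained the 20% dropout.
2. If the stated rates and significance level stand, say that 139 evaluable per group gives about 87% to 91% power, depending on method, for 11% versus 26% at two-sided 0.05, and that 80% power corresponds to about 11% versus 24%. If a rate, the significance level or the power was misstated, correct that figure instead. Name the formula either way.
3. Say that the 11% is PEth-based and that PEth abstinence is now secondary.
4. For the TLFB primary outcome, either state that the 11% is assumed to carry over, or show power for a 15-point difference over a range of TAU rates that includes 11%, with the method named or both methods shown, as in the last table above.

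The cost is a few sentences of protocol text and no change to enrolment, procedures or analysis.

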We will measure a range of pretreatment variables at baseline to ensure that participants meet eligibility criteria and that important predictor variables are measured (Table 3, Summary of Study Assessments). The baseline interview will include evaluations for alcohol, drug, and psychiatric disorders, and verify past 30-day laboratory values or collection of blood work (See Table 3). To avoid assessment reactivity,^{87,88} alcohol questions will be as brief as possible and interspersed among questions addressing other health-related domains. Using validated instruments at baseline, during treatment, and at end-of-treatment, we will examine the differential impact of CM plus stepped care on a range of measures. To minimize assessment reactivity, we will restrict assessments to those necessary and attempt to avoid those that would serve as motivation to change alcohol consumption. The primary study outcome, assessed at 6 months, was originally proportion of patients with PEth documented abstinence since this objective measure has advantages over self-report.⁸⁹ However, due to difficulty collecting PEth

during the COVID-19 pandemic, and on the recommendation of our DSMB, we changed the primary outcome to self-reported Timeline Follow Back at week 24. Abstinence confirmed by PEth was changed to a secondary outcome, Secondary study outcome, assessed at 3 months, will be proportion of patients with PEth documented abstinence. In addition, we will assess, at 6 months, alcohol consumption by TLFB and change in HIV biological markers as measured by viral load and VACS index. Exploratory analyses will evaluate the impact of CM plus stepped care on measures of medical conditions impacted by alcohol including exhaled CO, FIB-4, detectable HCV infection, depressive symptoms using the PHQ-9 and use of psychoactive medications that interact with alcohol.

Retention and Collection of Patient Locator Information

We use retention and tracking strategies developed to minimize attrition.^{90,91} We will obtain locator information on 5 individuals and update at each visit. RAs will notify patients by phone, text, mail and/or email before each assessment. We will contact other locators after 3 attempts and if unsuccessful we will send a registered letter. We couple research visits to scheduled medical visits when possible.

Study Period:

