Assessments at 9 and 12 months will include: PEth testing, pharmacy fill/refill data for ART, TLFB, VACS index, HRBS, ASI, PHQ-9, TSR, exhaled CO test or urine cotinine as indicated, HCV as indicated, past 30 day prescription of psychoactive medications that interact with alcohol. We will additionally assess measures of health care utilization (e.g. ED visits, hospitalizations, medications prescribed) based on the VA EMR or Epic. At the end of study participation all VA subjects will be offered enrollment in VACS for continued follow up.

Due to the declared public health emergency in March 2020, the assessments are done by videoconference or telephone. This will limit participants' and employees' exposure to possible COVID-19 exposure. Participants will receive \$50 upon completing the telephone assessment. We will ask participants to complete the visit when conditions permit them to come to the clinic to conduct laboratory and PEth testing.

Participant compensation for completing assessments

Participants will be compensated \$50 completing each assessment at baseline assessment, during treatment (3 months), end of treatment (6 months) and the follow-up assessment at 9 and 12-months. The total possible compensation for completing study assessments is \$250. Patients randomized to CM plus stepped care patients may earn more depending upon their response to treatment. In addition, patients randomized to CM plus stepped care will receive \$15.00 per intervention visit to cover travel costs.

1. Genetic Testing N/A

A. Describe

- i. the types of future research to be conducted using the materials, specifying if immortalization of cell lines, whole exome or genome sequencing, genome wide association studies, or animal studies are planned
- ii. the plan for the collection of material or the conditions under which material will be received
- iii. the types of information about the donor/individual contributors that will be entered into a database
- iv. the methods to uphold confidentiality

B. What are the conditions or procedures for sharing of materials and/or distributing for future research projects?

C. Is widespread sharing of materials planned?

D. When and under what conditions will materials be stripped of all identifiers?

E. Can donor-subjects withdraw their materials at any time, and/or withdraw the identifiers that connect them to their materials?

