A likelihood-based ignorable analysis using a generalized linear mixed model (GLMM) will be used to compare abstinence between groups.^{111,112} The primary advantage of the mixed model when compared to commonly used methods such as complete case analysis and single imputation (e.g. last observation carried forward) is its flexibility in handling missing data. This analysis makes use of all available outcome data at each timepoint and assumes that missing data occurs at random (i.e. not informative).¹¹³ The inclusion of 3, 6, 9 and 12 month outcome data in the model will assist in meeting this assumption. More specifically the mixed models will include fixed effects for intervention (CM plus stepped care vs. TAU), time (3, 6, 9, 12 months), and the interaction of intervention with time. Additional fixed effects will be included for baseline covariates: PEth, stratification group (at-risk drinking, medical condition impacted by alcohol, AUD), number of drinks per week, gender, VACS index and study site. Given the heterogeneity in the patient groups, the interaction between intervention and stratification group will be evaluated and included in the primary analysis at the p<0.10 significance level. Linear contrasts will be used to estimate intervention group differences and 95% confidence intervals at the primary 6-month outcome assessment. Similar contrasts will be performed at the other secondary follow-up times and supportive analyses examining the average and slope of change in abstinence rates across post-randomization time will be performed. Subgroup analyses will be performed to evaluate moderation of the intervention response by stratification group and study site. We will also use linear mixed effect models to compare continuous PEth and alcohol consumption using data from the TLFB.

Analysis for Aim 2: The primary objective of Aim 2 is to determine if HIV biomarkers (VACS index) differ between subjects receiving CM plus stepped care compared to those receiving TAU. The primary response will be defined as a 5-point improvement from baseline on the VACS index. As in Aim 1, a GLMM will be used to compare this response. We will use a repeated measures mixed model analysis with continuous VACS index as the outcome. As in Aim 1, we will perform subgroup analyses to evaluate moderators.

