Analysis for Exploratory Aims: For aim 3, we will evaluate the impact of the intervention in those with medical conditions on condition-specific outcomes such as HIV viral load, eCO or urine cotinine (for smoking cessation), FIB-4, detectable HCV virus, depressive symptoms and use of psychoactive medications that interact with alcohol. These analyses will focus on estimation rather than hypothesis testing and will be performed only in those identified with the specific medical condition at baseline. GLMMs will be used to describe these outcomes by treatment group and time. Treatment differences for continuous outcomes, odds ratios for dichotomous outcomes and rate ratios for count outcomes along with 95% CIs will be estimated.

Plan for Missing Data: Several strategies will be imposed to accommodate the likelihood of missing data. Prevention is the most effective manner to control bias and loss of power from missing data.¹¹⁴ In our prior alcohol trials we have obtained 6 month assessments in 95% and 88% of subjects.^{60,61} We will follow the intent to treat principle, requiring follow-up of all subjects randomized regardless of the treatment received.¹¹⁵ Telephone and text visit reminders will be sent to participants prior specified collection times. Timely data entry combined with weekly missing data reports will trigger protocols for tracking and obtaining missing data items. Despite these efforts it is reasonable to assume missing data will occur. Our primary analysis is valid under the assumption that missing data is missing at random (MAR).¹¹¹ We will evaluate the plausibility of this assumption by determining the extent of missing data and use logistic regression to identify factors associated with dropout. While we do not expect differential dropout rates between groups or high loss to follow-up, we will perform sensitivity analysis using pattern-mixture and selection models under missing not at random (MNAR) assumptions to examine the robustness of conclusions of the primary analysis to missing data.

Timeline and Milestones

SECTION VI: RESEARCH INVOLVING DRUGS, BIOLOGICS, RADIOTRACERS, PLACEBOS AND DEVICES

If this section (or one of its parts, A or B) is not applicable, state N/A and delete the rest of the section.

A. DRUGS, BIOLOGICS and RADIOTRACERS

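### Missing PEth is modelled without the follow-up TLFB, and the not-at-random sensitivity analyses did not follow PEth when it became a secondary outcome

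*Combined protocol and SAP*

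**What the plan says.** All references are to Section V of the combined protocol and SAP.

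- **Why PEth is secondary.** Assessments, Overview, explains the change of primary outcome to TLFB at week 24 with the words "However, due to difficulty collecting PEth", referring to the pandemic, and cites a DSMB recommendation.
- **How PEth is now collected.** Follow-up assessments moves the assessments to video or telephone. It then says of the remainder: "We will ask participants to complete the visit when conditions permit them to come to the clinic to conduct laboratory and PEth testing". No time window is given. The assessment schedule puts TLFB at the same visits as PEth, and the Summary of Study Assessments describes TLFB as web-based with a 30-day recall.
- **The model.** Analysis for Aim 1 (item 9, Statistical Considerations) gives one generalized linear mixed model (GLMM) for abstinence. It has terms for arm, visit and arm by visit, plus baseline PEth, stratum, weekly drinks, gender, VACS Index and site. On missing data it says: "This analysis makes use of all available outcome data at each timepoint and assumes that missing data occurs at random". The support offered for that assumption is the outcome's own values at 3, 6, 9 and 12 months.
- **Sensitivity analysis.** Plan for Missing Data adds a logistic regression for predictors of dropout, and pattern-mixture and selection models under missing-not-at-random (MNAR) assumptions, "to examine the robustness of conclusions of the primary analysis to missing data". Adequacy of sample size and Analysis for Aim 1 now define the primary analysis as self-reported abstinence on TLFB.

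**The concern.** A participant seen remotely can have a TLFB and no PEth at the same visit. That is not dropout, and the missing-data plan does not address it. The regression concerns dropout, the MNAR models concern the primary analysis, and the PEth model uses no post-baseline TLFB.

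If whether a PEth sample is obtained depends on current drinking, and TLFB carries information about current drinking, then the missing-at-random (MAR) assumption can hold given TLFB and still fail for the model as specified. Earlier and later PEth values recover only part of what is lost.

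The stake is the role PEth now plays. The primary outcome is self-report in a trial where one arm is rewarded for abstinence. Hypothesis 1a and the sample-size calculation are still written in terms of PEth. A PEth comparison that depends on who came back for the finger stick would be a weak check on the TLFB result.

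**Working it through.** **1. The plan's own figure.** Inputs from Statistical Considerations: "A type I error of 5% (two-sided) will be used to test for significance"; the TAU group of the earlier trials "reveals 11% spontaneous abstinence as assessed using PEth < 8 ng/ml at 6 months"; and the target, "To detect a 15% difference (proportion demonstrating abstinence in CM plus stepped care of 26%) with 80% power at a two-sided 0.05 significance level". The plan's result is 139 per group.

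Pooled two-proportion formula, with mean proportion 0.185:

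n = [z(α/2)·√(2·0.185·0.815) + z(β)·√(0.11·0.89 + 0.26·0.74)]² / 0.15²

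- 80% power: (1.960·0.5491 + 0.842·0.5388)² / 0.0225 ≈ 104.0, so 105 per group (117 with continuity correction).
- 90% power: (1.960·0.5491 + 1.282·0.5388)² / 0.0225 ≈ 138.7, so 139 per group.

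The stated 139 thus matches 90% power, not the stated 80%. With 20% dropout, 139/0.8 gives 174 per arm, or 348 in total, as the plan says. The power mismatch is a separate matter. Here it only shows that 139 observed PEth values per arm give about 90% power. From observed PEth alone, starting at 174 per arm, power is 90% at 20% missing, 80% at 40%, 73% at 50% and 63% at 60%.

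**2. Assumptions for the bias check.** The documents give no PEth missing rate, no mechanism and no PEth-TLFB agreement, so these are assumed:

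- true 6-month PEth abstinence of 11% and 26%, four visits, latent between-visit correlation 0.6;
- TLFB abstinence reported by 95% of PEth-negative and 20% of PEth-positive participants;
- 20% or 40% of 6-month PEth missing, and the other visits missing at random at the same rate;
- 6-month TLFB always present.

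An ignorable-likelihood fit to the four PEth visits stands in for the GLMM, without baseline covariates. It is run with and without 6-month TLFB abstinence, on 150,000 simulated participants per arm.

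**3. One case by hand.** CM arm, 40% missing, missingness odds three times higher in those not reporting abstinence:

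- Reporting abstinence: 0.26·0.95 + 0.74·0.20 = 0.395.
- Missing probabilities of 0.249 (abstinent by TLFB) and 0.499 (not) have odds ratio 3 and average 0.395·0.249 + 0.605·0.499 = 0.40.
- PEth-negative and observed: 0.26·(0.95·0.751 + 0.05·0.501) = 0.192.
- PEth-positive and observed: 0.74·(0.20·0.751 + 0.80·0.501) = 0.408.
- Observed abstinence: 0.192/0.600 = 32.0%, against a true 26%.

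In the simulation, borrowing from other PEth visits lowers this only to 30.8%. Adding TLFB returns 26.0%.

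**4. Difference between arms (simulated).**

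| Missingness | Missing | True | PEth only | With TLFB | Bias, PEth only (points) |
|---|---|---|---|---|---|
| Unrelated to drinking | 40% | 0.154 | 0.154 | 0.154 | 0 |
| Unrelated, 50% TAU / 30% CM | as shown | 0.150 | 0.151 | 0.151 | about 0 |
| By TLFB, OR 2, both arms | 20% | 0.149 | 0.156 | 0.149 | +0.7 |
| By TLFB, OR 3, CM only | 20% | 0.152 | 0.174 | 0.153 | +2.2 |
| By TLFB, OR 2, both arms | 40% | 0.152 | 0.166 | 0.151 | +1.4 |
| By TLFB, OR 3, both arms | 40% | 0.148 | 0.170 | 0.148 | +2.2 |
| By TLFB, OR 3, CM only | 40% | 0.151 | 0.199 | 0.151 | +4.8 |
| By TLFB, OR 3, TAU only | 40% | 0.151 | 0.125 | 0.150 | -2.6 |
| By true PEth (MNAR), OR 3, both arms | 40% | 0.149 | 0.178 | 0.161 | +2.9 |
| By true PEth (MNAR), OR 3, CM only | 40% | 0.148 | 0.209 | 0.180 | +6.1 |

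In the last two rows TLFB leaves +1.2 and +3.2 points, so it does not replace an MNAR analysis.

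**5. Precision.** This used 174 per arm, missingness unrelated to anything, 400 simulated trials per setting, and three assumed PEth-TLFB agreements (95%/20%, 95%/10%, 90%/35%). Adding TLFB cuts the variance of the difference by about 4-10% at 20% missing, 4-21% at 40% and 8-31% at 60%. At 40% missing and 95%/20% agreement, the PEth-only standard error is about 5.2 points.

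**The case against.** The strongest reply is that the documents describe logistical missingness. Testing was paused for safety and resumed when sites allowed. Nothing says that drinkers were less likely to return, and no missing rate is given. A reader might infer that the PEth estimate is biased. The documents do not support that: purely logistical missingness gives no bias even at unequal rates by arm, and the biased rows above follow from an assumed mechanism. In the rows driven by TLFB, recovery by TLFB is also partly built in. This objection stands, and it limits the claim to openness to bias. It does not touch the precision loss or the scope of the MNAR analyses.

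Three other strong readings also fail.

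- The model does not use PEth alone. Baseline drinks per week and the other covariates are in it, and the stand-in fit omitted them, so the real bias could differ.
- The plan does not lack MNAR methods. It has them, and their wording was not extended when the outcomes were exchanged.
- PEth below 8 ng/ml is not the only objective measure. Continuous PEth is also modelled, with the same gap, and breath or saliva tests are scheduled, though no analysis of them is stated.

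The last objection is to the remedy. Imputing the biomarker from self-report brings back some of what PEth was meant to avoid. A deferred sample, which reflects about the past 21 days, may also not overlap the 30-day TLFB of the remote visit. Both points stand. They are reasons to place the TLFB-based analysis beside the GLMM and not in its place.

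**Conclusion.** The point holds in limited form, as a cheap improvement. Followed as written, the plan gives its main objective check on a self-reported primary outcome no MNAR analysis, and it leaves scheduled follow-up TLFB data out of the PEth model.

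Under the assumptions above (20-40% missing, odds ratio 2-3 by reported drinking), the bias in a true 15-point difference is about +0.7 to +5 points, or about -2.6 points if only TAU is affected. At 40% missing and a standard error near 5.2 points, the upward biases of 1.4 to 4.8 points are roughly 0.3 to 0.9 standard errors. The bias is zero if missingness is purely logistical. The precision cost of about 4-31% of variance at 20-60% missing needs no informative mechanism, but its size depends on the assumed PEth-TLFB agreement.

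Whether there is any bias, and how much, cannot be settled from the documents.

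**What to change.** 1. **Extend the MNAR analyses to PEth.** State in Plan for Missing Data that they also cover PEth below 8 ng/ml at 6 months. Include a tipping-point analysis with a separate delta for each arm, reporting the combinations at which the conclusion changes.
2. **Add one prespecified analysis beside the Aim 1 GLMM.** Use multiple imputation by arm, or a joint model. Include post-baseline TLFB abstinence and drinks per week, all observed PEth values, a remote-period indicator and the planned baseline covariates, then apply the planned 6-month contrast. Imputing by arm matters because self-report accuracy may differ between arms.
3. **Model missing PEth as well as dropout.** Run the planned missingness regression on missing PEth too. In the imputation, use only TLFB data whose recall period matches the actual date of the PEth sample.

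The cost is SAP wording and modest programming, using data already scheduled for collection. The downside is that an imputation model must be specified and defended. It leans partly on self-report, so it supports the GLMM and does not replace it.
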